### **Data analysis:**

Each variable was inspected for extreme outliers (i.e., data points that fell more than 4 standard deviations [SD] away from the mean) using summary statistics and box plots. An extreme outlier was excluded from the final analysis. Normality of the variables was determined based on skewness and kurtosis. Number that is greater than +1 or lower than -1 indicate a substantially skewed distribution. For kurtosis, if the number is greater than +1, the distribution is too peaked and less than -1 indicates a distribution that is too flat. If the distribution was found to deviate from normality, non-parametric statistical analysis was conducted.

Descriptive statistics described the study sample for age, sex, height, weight, race, current medication, education level, exercise level, DHI, ABC, history of falls, MoCA and HI- MoCA. To determine if the groups are similar with respect to background measures and demographics a comparison of the three groups Normal hearing, Mild BHL and > Moderate BHL (moderate, moderately-severe, severe and profound) was done using one-way analysis of variance (ANOVA) or non-parametric Kruskal-Wallis Test for continuous measures and Chi-square analyses for categorical measures (e.g., gender).

For Aim #1: Compare single task (=ST) gait parameters between individuals age and education-matched with Mild BHL, > Moderate BHL and controls with Normal hearing and Aim #3: Compare the effect of a cognitive task on gait parameters (=DT) between age and education-matched people with Mild BHL, > Moderate BHL and control with Normal hearing: For the primary outcome measure, gait speed and its variability, and secondary outcome measures (stride length, stride time and their variability) during the 1-min walk, a mixed model repeated measures (RM)- ANOVA was conducted with 1 within-factor (task) of 2 levels (ST and DT ['subtraction 3']) and 1 between factor (group) of 3 levels (Normal hearing, Mild BHL, Moderate BHL). When the distributions were found to deviate from normality the Kruskal-Wallis' test was conducted for a between-group comparison and the Wilcoxon signed-rank test for a within-group comparison. Since I had a significant difference with age, I adjusted for age the ANOVA comparison.

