Partial Eta Square (PET) Effect Size was reported for each main effect and interaction (small effect, PET  $\geq 0.08$ ; middle effect, PET  $\geq 0.20$ ; and high effect, PET  $\geq 0.32$ ). P-values with a value of  $p < 0.05$  were considered statistically significant. Bonferroni corrections were applied to post hoc comparisons as applicable.

For Aim #2: Compare cognitive function (i.e., the Neurocognitive Index) between individuals age and education-matched with Mild BHL, > Moderate BHL and controls with Normal hearing. One way ANOVA (or non-parametric Kruskal-Wallis Test) was used to compare the Neurocognitive Index between the three groups. Moreover, one way ANOVA (or non-parametric Kruskal-Wallis Test) was used to compare the secondary outcome measures, i.e., Composite Memory, Verbal Memory, Visual Memory, EF, Cognitive Flexibility, Complex RT, Working Memory and Sustained Attention and the cognitive ST and DT performance. I used one-way ANOVA with the dependent variable, the cognitive domain (Neurocognitive Index or any of the secondary outcome measures), and group as independent variable. For the raw scores I used the ACNOVA to adjust for age since we had significant age difference and these results do not present an age-matched score. Cohen's d effect size was calculated per comparison and was defined 'small' effect size as  $d = 0.2$ , 'medium' effect size as  $d = 0.5$  and a 'large' effect size as  $d = 0.8$ .

For Aim #4: Explore whether cognitive performance (i.e., the Neurocognitive Index) is correlated with DTC per group. One way ANOVA (or non-parametric Kruskal-Wallis Test) was used to compare the DTC between the three groups. Correlations between the cognitive domains and DTC were assessed using Pearson's correlation (or its non-parametric equivalent Spearman's, if the distributions are found to deviate from normality) for continuous variables. Pearson's correlation for each comparison was defined as 'little to none' for  $r = 0-0.24$ , 'fair' for  $r = 0.25-0.49$ , 'moderate to good' for  $r = 0.50-0.74$  and 'good to excellent' for  $r = 0.75-1.00$ . SPSS version 27 IBM (NY, US) was used for all statistical analysis.

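### Gait variables that fail the ±1 normality screen move to Kruskal-Wallis, which cannot carry the age adjustment given to the ANOVA

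*Combined protocol and SAP*

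**What the plan says.** All of this is in the Data analysis section of the combined protocol and SAP.

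- **Screening.** Points more than 4 SD from the mean are removed ("An extreme outlier was excluded from the final analysis"). Each variable is then judged on skewness and kurtosis against limits of ±1. "If the distribution was found to deviate from normality, non-parametric statistical analysis was conducted".
- **Aims 1 and 3, parametric branch.** A mixed repeated-measures ANOVA has task (single task, dual task with subtraction by 3) as the within factor and three hearing groups as the between factor. The outcomes include the primary one ("For the primary outcome measure, gait speed and its variability"). Age was added: "Since I had a significant difference with age, I adjusted for age the ANOVA comparison". The interaction is covered: "Partial Eta Square (PET) Effect Size was reported for each main effect and interaction".
- **Aims 1 and 3, rank branch.** The Kruskal-Wallis "test was conducted for a between-group comparison and the Wilcoxon signed-rank test for a within-group comparison". Nothing further is named.
- **Aim 2.** Age adjustment is mentioned once more, for an ANCOVA on raw cognitive scores.
- **Aim 4.** The stated purpose is "Explore whether cognitive performance (i.e., the Neurocognitive Index) is correlated with DTC per group". DTC is also compared across the three groups by one-way ANOVA or Kruskal-Wallis. The abbreviation is not expanded or defined, and no age adjustment is stated.

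**The concern.** The aims describe age-matched groups, but the author found a significant age difference and thought it important enough to adjust for. Whether a gait variable keeps that adjustment then depends on the shape of its distribution. Skewness does nothing to remove confounding by age. A variable that fails the screen moves from an age-adjusted comparison to one that has no place for a covariate. If gait varies with age, a hearing-group difference on that branch may be an age difference. The list of eligible variables includes the primary outcome.

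The secondary matter is Aim 3, which is to "Compare the effect of a cognitive task on gait parameters (=DT) between age and education-matched people". That is a group-by-task question. The ANOVA answers it through the interaction. The rank branch names no counterpart and does not say whether Kruskal-Wallis was run on the single-task value, the dual-task value or the change.

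**Working it through.** **No plan figure to reproduce.** The Data analysis section gives no sample size, SD, age gap or age-gait correlation. Every numerical input below is an assumption except the 0.05 level, the ±1 limits and the 4 SD rule.

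**Step 1: which tests can carry age.**

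| Analysis in the plan | Can adjust for age? | Adjustment stated? |
|---|---|---|
| Repeated-measures ANOVA, gait | yes | yes |
| Kruskal-Wallis between groups, gait | no | no |
| Wilcoxon signed-rank within group, gait | not needed: each person is compared with themselves | no |
| DTC across groups, ANOVA or Kruskal-Wallis | ANOVA yes, Kruskal-Wallis no | no |

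**Step 2: false positives from age alone.** Three groups of n (g = 0, 1, 2), no hearing effect, age spread s between the extreme groups, within-group age-gait correlation ρ:

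- age = Z + s·g/2
- log(outcome) = 0.4·[ρ·age + √(1 − ρ²)·e], with Z and e standard normal.

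The apparent hearing difference between the extreme groups is ρ·s in SD units of log outcome: from 0.3 × 0.5 = 0.15 to 0.5 × 1.0 = 0.50. Kruskal-Wallis uses ranks only, so the log-normal shape does not affect its rate. Rejection at p < 0.05, 3,000 runs per row (rank ANCOVA regressed the ranked outcome on ranked age and group):

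| n per group | ρ | s (SD) | Kruskal-Wallis | Rank ANCOVA |
|---|---|---|---|---|
| 15 | 0.3 | 0.5 | 5.7% | 4.6% |
| 15 | 0.3 | 1.0 | 10.2% | 5.4% |
| 15 | 0.5 | 0.5 | 8.1% | 5.4% |
| 15 | 0.5 | 1.0 | 19.6% | 5.6% |
| 20 | 0.3 | 0.5 | 6.1% | 5.2% |
| 20 | 0.3 | 1.0 | 11.5% | 5.5% |
| 20 | 0.5 | 0.5 | 9.4% | 5.4% |
| 20 | 0.5 | 1.0 | 24.1% | 5.5% |
| 30 | 0.3 | 0.5 | 8.0% | 5.2% |
| 30 | 0.3 | 1.0 | 14.3% | 4.9% |
| 30 | 0.5 | 0.5 | 12.2% | 5.7% |
| 30 | 0.5 | 1.0 | 35.8% | 5.2% |

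**Step 3: condition on what the author reports.** With evenly spaced group means, the ANOVA on age gives F = n·s²/4. Significance at 0.05 therefore needs an observed spread of √(4F/n), which is 0.93, 0.79 and 0.64 SD for n = 15, 20 and 30. Among simulated trials with a significant age difference (20,000 runs per setting before selection), Kruskal-Wallis rejects in 9–25%, 10–28% and 10–38% respectively. Age-adjusted analysis stays at 5–6%.

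**Step 4: how often the screen diverts a variable.** After the 4 SD exclusion, with the rule applied to pooled data (the plan does not say pooled or per group), total N = 45, 60 and 90:

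- truly normal variable: 10%, 7%, 4%
- log-normal variable with log-SD 0.4: 49%, 51%, 52% (18–70% over log-SD 0.2 to 0.5).

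**Step 5: a task-cost comparison.** In trials with a significant age difference, unadjusted Kruskal-Wallis on dual minus single task rejects in 4–5% if the change is unrelated to age. If the change correlates 0.2 to 0.5 with age, it rejects in 7–24%, 7–29% and 8–38% for n = 15, 20 and 30, against 5% for rank ANCOVA. Scale also matters. When every group has the same proportional task effect but groups differ in level, rank ANCOVA on the raw difference rejected in 6–12% of runs, against 4–6% for log(DT) − log(ST).

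**The case against.** The rank branch is conditional and the section is a past-tense account of a pilot study. No distributions or results are given, so perhaps no gait variable took this branch; the ANOVA branch already covers both age and the interaction. This stands as a limit on reach: the gap lies in the rule and its reporting, and no result is shown to be wrong. A reader might infer that the primary gait-speed result is confounded by age. The documents do not support that.

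No sentence says that Kruskal-Wallis was left unadjusted. That also stands, and the point is an inference. It is a strong one, because the test takes no covariate and no age-adjusted rank method is named anywhere.

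On Aim 3, the Aim 4 comparison of DTC largely supplies the group-by-task test if DTC is the change from single to dual task. Most of this stands. A reader might infer that Aim 3 has no such test on the rank branch, or that it was answered by Kruskal-Wallis on dual-task values or by comparing separate Wilcoxon results. The text says none of these. What remains is that DTC is undefined and tied to no gait parameter. The protocol also has a dual-task TUG, subtraction by 1 and by 3, and cognitive performance under both conditions, so the term could refer to more than one quantity. Its comparison has no stated age adjustment.

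Finally, the magnitudes rest on assumed inputs, and the low end is close to nominal. That is correct; they show direction and possible range only.

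**Conclusion.** The age point holds and should be fixed. The rule sends any gait variable outside ±1, possibly a primary one, to a between-group test that cannot adjust for the age difference the author reports. Under the assumed inputs the false-positive rate is about 6% to 36% unadjusted, against about 5% to 6% with age adjustment. The low end is trivial and the high end is about seven times nominal (35.8/5 = 7.2). The effect in this study is unknown, because neither the variables on the rank branch nor the inputs are reported. The Wilcoxon tests are not open to the age criticism. The Aim 3 point is secondary and is mainly one of definition and cross-reference, although the DTC comparison is protected from age only if task cost does not depend on age.

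**What to change.** 1. For gait variables that fail the rule, replace unadjusted Kruskal-Wallis with one method, fixed in writing before the re-run: ANCOVA on ranks with age as covariate. Offering a choice between ranks and logs would add analyst freedom.
2. Aim 1: apply it to the single-task value.
3. Aim 3: apply it to a per-participant task cost on a relative scale, either log(DT) − log(ST) or percent change, with one of these chosen and each gait parameter named. Define DTC as that quantity and adjust its group comparison for age.
4. Keep Wilcoxon only to describe the task effect within each group.
5. State which variables took the rank branch.

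The cost is revised wording and a short re-run on existing data; age is already collected. Some p-values will change, and results on this branch are read on a rank scale.

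### The plan does not say how age entered the age-adjusted gait RM-ANOVA; if it was in uncentred years with a task-by-age term, the reported task main effect refers to age 0

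*Combined protocol and SAP*

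**What the plan says.** Under Data analysis, the paragraph on Aims #1 and #3 covers the main gait outcomes: "For the primary outcome measure, gait speed and its variability, and secondary outcome measures (stride length, stride time and their variability"). The model is described as follows: "a mixed model repeated measures (RM)- ANOVA was conducted with 1 within-factor (task) of 2 levels (ST and DT ['subtraction 3"]), crossed with "1 between factor (group) of 3 levels (Normal hearing, Mild BHL, Moderate BHL"). The paragraph ends by noting that age differed significantly, and for that reason: "I adjusted for age the ANOVA comparison".

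The next paragraph adds: "Partial Eta Square (PET) Effect Size was reported for each main effect and interaction". It grades those effect sizes as small from 0.08, middle from 0.20 and high from 0.32, and sets the significance threshold at p < 0.05. Task is one of the two main effects in this model, so its effect size is a reported result. On software, the plan says only: "SPSS version 27 IBM (NY, US) was used for all statistical analysis".

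Three things are not stated: whether age was centred, whether a task-by-age term was in the model, and whether the task effect was taken from the age-adjusted or the unadjusted model.

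**The concern.** In a repeated-measures ANOVA without a covariate, the task main effect is the average single-to-dual-task change in the sample. Once a covariate is added and allowed to interact with task, that row of the output changes meaning: it becomes the change at covariate value zero. Mean-centring puts zero at the average participant. In plain years, zero is a newborn, far outside any sample that could do this walking test.

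What is at stake is one reported test and one effect size per gait outcome, the primary outcome included. That row tells the reader whether the subtraction task altered gait at all, which is the background for reading group differences in the dual-task effect. A small or non-significant task effect printed beside clearly different single- and dual-task marginal means, evaluated at mean age, would be confusing, and nothing in the plan would let a reader resolve it.

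**Working it through.** The plan gives no sample size, ages, age SD, gait effect or SD of change, so it has no figure to reproduce. The design (two task levels, three groups, age adjustment, 0.05 threshold, partial eta squared) comes from Data analysis. Every numerical input below is an assumption.

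**1. What the task row tests.** With two task levels, the within-participant part of the model is a regression of d = DT − ST:

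d = b0 + (sum-to-zero group codes) + b3 × age + error, with n − 4 residual degrees of freedom.

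The task main effect is the test of b0, the mean of d at age = 0. The group-by-task interaction is the joint test of the group codes. Replacing age by age minus its mean changes b0 only.

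**2. Standard error.** With equal groups, the variance of b0 is approximately (s²/n) × [1 + (mean age / within-group age SD)²]. The SE is therefore multiplied by √(1 + (mean/SD)²):

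- mean 40, SD 16: √(1 + 2.5²) = 2.7
- mean 51, SD 13: √(1 + 3.92²) = 4.05
- mean 65, SD 11: √(1 + 5.91²) = 6.0

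**3. Worked case.** Assume 20 per group (n = 60), group mean ages 45/50/58 (mean 51), SD 13, slowing of 0.15 m/s at mean age and SD of change 0.15 m/s.

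- Centred: SE = 0.15/√60 = 0.0194; effect/SE = 0.15/0.0194 = 7.7; power about 100%.
- Uncentred, no true age slope: SE = 0.0194 × 4.05 = 0.078; effect/SE = 0.15/0.078 = 1.9; power 47% from the noncentral F with 1 and 56 df, and 45% by simulation (4,000 data sets).
- Uncentred, slowing larger by 0.002 m/s per year of age: the quantity tested is −0.15 + 0.002 × 51 = −0.05 m/s; effect/SE is about 0.6; power 8% to 9%. Centred, the estimate stays at −0.15 and power at about 100%.

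**4. Separate simulation, other assumptions.** 2,000 runs per scenario; true task effect of 1 SD of the change at mean age. The first two rows use 20 per group, group mean ages 60/64/68 and age SD 8.

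| Task-by-age slope (SD per 10 years) | Power, uncentred | Power, centred | Mean partial eta², uncentred | Mean partial eta², centred |
|---|---|---|---|---|
| 0 | 0.138 | 1.000 | 0.030 | 0.518 |
| −0.1 | 0.058 | 1.000 | 0.019 | 0.518 |
| Range over all 18 scenarios | 0.04–0.51 | 1.000 | 0.01–0.07 | 0.51–0.53 |

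The 18 scenarios use 15, 20 or 30 per group, group mean ages 60/64/68 (SD 8) or 45/55/65 (SD 12), and slopes of 0, −0.1 or −0.2. On the plan's own scale, an effect that is high when centred falls below small when uncentred. With no age in the model, the first row gives power 1.000 and partial eta² 0.514.

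**5. The error can run the other way.** With no task effect at age 64 and slopes of −0.1, −0.3 and −0.5 SD per 10 years (20 per group, ages 60/64/68, SD 8), the uncentred task test gave p < 0.05 in 9%, 42% and 82% of runs. Centred, it did so in 4%, 5% and 7%. The slight rise to 7% arises because centring is at each sample's own mean age, which is not exactly 64.

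**6. What does not move.** The group-by-task p-value was the same under both codings in every run (largest difference about 6 × 10⁻¹⁴, rounding error). The group main effect is likewise a contrast among groups at a common age and does not depend on where zero lies.

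SPSS itself was not run. The result is algebraic, and the simulations illustrate its size.

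**The case against.** The strongest reply is that the premise is not in the documents. The plan says "I adjusted for age the ANOVA comparison" and no more. A reader might infer that age was entered in raw years and that the reported task p-value and effect size are therefore wrong. The text does not support that. It does not say that age was uncentred, and naming SPSS 27 does not settle the procedure or whether a task-by-age term was fitted. If age was centred, or entered without that term, the problem does not arise. The adjustment may also have been meant only for the between-group comparison, with the task row taken from the unadjusted model. This objection stands, and it makes the point conditional.

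The second reply concerns the aims. A reader might take Aim #3 to be about the task effect as such, and so to be at risk. Its wording is "Compare the effect of a cognitive task on gait parameters (=DT) between age and education-matched people" with different hearing status, which is the group-by-task term. Aim #1 is also a between-group comparison. Neither answer changes with centring. This stands too.

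Third, other analyses limit the exposure. Outcomes that fail the skewness and kurtosis rule go to the Wilcoxon signed-rank test for the within-group comparison, which carries no covariate. Dual-task cost is compared between groups under Aim #4 with no age covariate stated. Marginal means evaluated at mean age are unaffected.

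Fourth, every magnitude rests on chosen inputs. That is true, but the direction does not depend on them: the SE factor in step 2 exceeds 1 for any adult sample.

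What survives is that the plan undertakes to report an effect size for the task main effect without giving the reader a way to know which age it refers to.

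**Conclusion.** The point holds conditionally. If age entered the RM-ANOVA in uncentred years together with a task-by-age term, and the task row was taken from that model, the reported task main effect and its partial eta squared describe age 0. They could be missed, mis-sized or falsely significant. The plan neither confirms nor excludes this.

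Under the worked assumptions, power for the task effect falls from about 100% to about 45%, and to 8% to 9% if slowing increases modestly with age. Over the wider set of assumptions in step 4, uncentred power lies between 0.04 and 0.51. None of these figures describes the actual study, whose ages and sample size are not given.

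The consequence is confined to the task main effect for each gait outcome. It gives no reason to doubt the between-group tests for Aims #1 and #3. Severity is minor, but the correction is free and protects a reported result for the primary outcome.

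**What to change.** Subtract the overall sample mean age from each participant's age before entering it in every age-adjusted RM-ANOVA, or take the task main effect from the model without age. State in Data analysis which was done, whether task-by-age was fitted, and which model supplies the reported task effect. If task-by-age is fitted, report it, since it shows how far the task effect depends on age.

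If the analysis has already been run with centred age or without the task-by-age term, a sentence saying so is enough. Otherwise the cost is one line of syntax, a rerun and that sentence. No new data are needed, the group and group-by-task tests do not change, and there is no statistical downside.

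### Bonferroni for post hoc group comparisons is valid, but with three groups closed testing or Holm controls the same family-wise error with more power: a cheap improvement, not an error

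*Combined protocol and SAP*

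**What the plan says.** All of this is in the Data analysis section of the combined protocol and SAP.

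- **Groups.** The gait model for Aims 1 and 3, which holds the primary outcome, has "1 between factor (group) of 3 levels (Normal hearing, Mild BHL, Moderate BHL"), crossed with "1 within-factor (task) of 2 levels (ST and DT ['subtraction 3"]). It is a 2 × 3 mixed repeated-measures ANOVA, with Kruskal-Wallis and Wilcoxon signed-rank tests as the non-normal fallback.
- **One-way tests.** For Aim 2, "One way ANOVA (or non-parametric Kruskal-Wallis Test) was used to compare the Neurocognitive Index between the three groups". The dual-task cost (DTC) comparison in Aim 4 has the same form.
- **Level.** P-values below 0.05 "were considered statistically significant".
- **Post hoc rule.** "Bonferroni corrections were applied to post hoc comparisons as applicable". The text does not say which comparisons form a family, what the divisor is, or whether a significant omnibus test must come first.

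No sample size, SD, target difference or power is stated. The section is in the past tense.

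**The concern.** Whether mild hearing loss already differs from normal hearing, or only moderate and worse loss does, is answered by the pairwise contrasts and not by the three-group test. In a pilot those contrasts are likely to have limited power. If the post hoc tests follow a significant three-group test, dividing 0.05 by three asks for more protection than three groups need, and real contrasts may be reported as no difference. Even without such a gate, a step-down rule is available that never rejects less than Bonferroni.

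**Working it through.** **1. Inputs.** From the documents: level 0.05 and three groups, hence 3 × 2 / 2 = 3 pairs and a Bonferroni level of 0.05 / 3 = 0.0167. Assumed, because the documents are silent: two-sided tests, equal groups of 8 to 40, SD 1, normal data, and mean patterns (0, 0, d) and (0, d/2, d) with d from 0.2 to 1.2. The plan has no power figure to reproduce. One-way results below are simulated with pooled-variance pairwise tests.

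**2. Why 0.05 per pair is enough after the gate.** Three means leave three cases:
- All equal: a false claim first needs a false omnibus rejection, which has probability 0.05.
- Exactly two equal: only one pairwise null is true, and it is tested at 0.05.
- All different: no pairwise null is true.

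Family-wise error is therefore at most 0.05 in every case.

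**3. Simulated family-wise error, one-way, n = 10 to 30 per group.**

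| Rule | All means equal | One group apart |
|---|---|---|
| Omnibus gate, then Bonferroni | 0.041–0.042 | 0.016–0.017 |
| Omnibus gate, then each pair at 0.05 (closed) | 0.049–0.050 | 0.047–0.050 |
| Each pair at 0.05, no gate | 0.117–0.121 | not needed |

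The unused error in the first row is the lost power. The last row shows that the shortcut needs the gate. As a rough check, three independent tests would give 1 − 0.95³ = 0.143.

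**4. Power at d = 0.8, Bonferroni to closed testing.**

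| n per group | One group apart, each true pair | Evenly spaced, largest pair | Evenly spaced, Normal v Mild: gain |
|---|---|---|---|
| 15 | 0.39 to 0.49 | 0.388 to 0.440 | 7.5 points |
| 20 | 0.528 to 0.638 | 0.523 to 0.574 | 9.7 points |
| 30 | 0.74 to 0.84 | 0.737 to 0.774 | 13.3 points |

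The evenly spaced columns use Bonferroni with the omnibus gate. Against Bonferroni without a gate, the largest-pair gain is 3.3 to 4.9 points. At n = 20 with one group apart, Holm gives 0.56 per true pair (about 3 points more than Bonferroni), and the chance of finding both true differences is 0.37 with Bonferroni, 0.43 with Holm and 0.55 with closed testing. For the largest of three evenly spaced means Holm gains only 0.7 to 1.0 points. Over the whole grid (n 8 to 40, d 0.2 to 1.2) the gain from closed testing runs from about 0 to 17 points.

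**5. The gait model.** With two task levels, the group-by-task F is the one-way F on each person's DT − ST difference. That gives three contrasts, and the shortcut holds: simulated family-wise error is 0.045 to 0.052 (n = 20, within-person correlation 0.5 and 0.8). If one group shifts by 0.6 SD under dual task only, pair power rises from about 0.29 to 0.38 (correlation 0.5) and from 0.70 to 0.80 (correlation 0.8).

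Group comparisons within ST and within DT are different: there are six pairs. With one group 1.2 SD apart under DT only, family-wise error is:
- pairs at 0.05 after a significant interaction: 0.145–0.152;
- the same with a per-task omnibus gate added: 0.087–0.091;
- 0.05/3 within each task: 0.054–0.056.

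**6. Unequal variances.** With n = 20, SDs 1/1/1.5, Normal far from the other two groups and those two equal, pooled-variance pairs give about 6.8% error under closed testing and equally under Holm, against 2.6–2.7% for Bonferroni. With SDs 1/1/2, closed testing gives 8.3% against 3.3%.

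**The case against.** The case for leaving the sentence alone has several parts.

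- **Nothing is wrong with Bonferroni.** This stands. A reader might infer that the plan contains an error; it does not. The choice is conservative.
- **The gate is inferred.** A reader might infer that the plan corrects twice, once by the omnibus test and again by Bonferroni. The sentence does not say that the post hoc tests wait for a significant omnibus test, so this cannot be asserted. It limits closed testing to places where the gate is written in. It does not touch Holm.
- **No fixed loss can be attached to this plan.** This also stands. A reader might want one figure for power given away, but without a sample size or effect any figure is conditional.
- **The shortcut does not reach every primary comparison.** A reader might extend 0.05 per pair to all post hoc tests. For group comparisons within a task, error would rise to about 0.15. Aim 1 concerns single-task gait, so its own pairwise question falls here and gains only what Holm offers.
- **Bonferroni leaves margin.** The group labelled > Moderate pools moderate through profound loss, so unequal spread is plausible, and both alternatives lose protection against it. Welch-type tests address this. The Kruskal-Wallis route was not simulated.
- **Timing and priority.** A more liberal rule adopted after the data were seen is a post hoc change. Bonferroni is also the only multiplicity control the section describes, with nothing across outcomes. Both points argue for labelling and low priority, not for rejecting the idea.

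**Conclusion.** The point holds as an efficiency suggestion. For three contrasts of one term after that term's significant three-group test, 0.05 per pair controls family-wise error at 5% and rejects everything that gated Bonferroni rejects. For any other family, Holm does the same relative to ungated Bonferroni. (Closed testing can occasionally miss a pair that ungated Bonferroni would catch, when the omnibus test fails, but its pairwise power was higher on average in the settings tabulated above.)

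At an assumed 15 to 30 per group and a largest difference of 0.8 SD, the gain is roughly 3 to 11 points for the largest difference and 7 to 14 for adjacent pairs under closed testing, and about 1 to 6 under Holm. Small effects or already high power shrink it towards zero. These figures assume normal data, equal group sizes and equal variances. The documents support neither a claim of error nor a plan-specific loss.

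**What to change.** Replace the post hoc sentence with wording such as:

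> For each term with a significant three-group omnibus test (the one-way tests of Aim 2 and DTC, the group main effect, and the group-by-task interaction tested as group contrasts of DT minus ST), the three pairwise group contrasts for that term are each tested at 0.05 (closed testing). For any other family, including group comparisons within ST or within DT, or where no omnibus test precedes, Holm replaces Bonferroni. If group variances differ, Welch-type omnibus and pairwise tests are used.

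List the members of each Holm family; if the ST and DT group comparisons are read together, that is six. This also supplies the family and gate that the present sentence leaves open.

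Because the analysis is reported as done, mark the rule as a change and show its results beside the Bonferroni results, or adopt it for the follow-on study. It should not silently replace what was reported.

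The cost is a few lines of text and a second column of p-values. The downsides are less margin against unequal variances, and simultaneous confidence intervals, if wanted, still need a single-step adjustment.
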